### **Primary outcome**

The rate of seroconversion of specific neutralizing antibodies against each HPV vaccine genotypes (6/11/16/18/31/33/45/52/58) at month 7 (which will be one month after either two doses of vaccine in ARM A or completion of a three doses schedule (0, 2 and 6 months) in ARM B) in women seronegative at baseline for these antibodies. The measure will be performed on a 10 ml tube by cLIA technique in Merck laboratory (see material and methods) [30,31]. Non inferiority of ARM A compared to ARM B will be reached if for each HPV genotype contained in the vaccine, at least 80% of the patients have a seroconversion rate. **We will analyze the results in intention-to-treat on the randomized cohort (n=102), and in On-treatment on the whole cohort (n=169).**

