**Primary outcome**

Rate of seroconversion of neutralizing antibodies against each HPV vaccine genotypes namely 6/11/16/18/31/33/45/52/58 among women seronegative at baseline for HPV vaccine genotypes, by measuring neutralizing antibody against the 9 vaccine genotypes of HPV at baseline, month 7. Comparison of that rate at month 7 (non inferiority defined as at least 80% of seroconversion in ARM A).

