Antibodies title peaks one month after last vaccine dose than decrease to a plateau and stabilize around month 12 after receiving the last dose. In this study, antibodies against HPV will be measured at baseline, month 7 (that is to say 1 month after receiving 2 or 3 doses depending in which arm the patient has been randomized to) and month 18 (or 12 months after receiving the second or third dose, reflecting the stabilized antibodies level. We expect that two doses of vaccine in HIV-positive patients with well controlled HIV viremia under cART for at least 6 months could induce seroconversion in at least 80% of the patients seronegative at baseline whereas the seroconversion rate is expected to be 95% after 3 doses according to previous studies using the quadrivalent vaccine in HIV-positive patients. We find a minimum of 80% efficacy in the two doses arm acceptable as in this arm the vaccine costs would decrease by 33%, administration will be easier, the risk of local reaction after injection could also be decreased and compliance with the whole vaccine administration could be improved.

Regarding the number of patients that should be enrolled in the study, we considered a sample size calculation based on the SAS 9.4 program for comparing two independent proportions (1:1 allocation in a non-inferiority trial) by a Pearson Chi-square test. If we consider 95% rate of seroconversion for ARM B (3 doses vaccines) and 80% for ARM A (2 doses vaccines) with a significance level test of 0.05 (alpha) and an 80% statistical power (Beta), we found that 60 patients per

arm would be needed (120 patients in total). We would then need in total 150 women to be randomized taking into account the possibility of follow-up lost.

The purpose of vaccinating women is to induce antibody response against each HPV genotype contained in the vaccine and in particular against the 7 high-risk genotypes that induces cancer. If, after 2 doses of vaccine (ARM A), the month 7 antibodies measure shows absence of seroconversion against one of the HPV genotypes contained in the vaccine, the participant will receive a third booster dose of Gardasil9.

In order to assess long term persistence of HPV-specific antibody responses, the follow up will be prolonged to the following time points after completion of the vaccine administration : 24, 36, 48 and 60 months.

The role of basal immune activation on seroconversion rate and long term persistence of antibody responses, will be assessed.

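### The stated 80% power belongs to one test of difference (95% v 80%), not to the success rule, which needs at least 80% seroconversion in ARM A for all nine genotypes

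*Protocol*

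**What the plan says.** The success rule is in the protocol's Primary outcome section: "Non inferiority of ARM A compared to ARM B will be reached if for each HPV genotype contained in the vaccine, at least 80"% of patients seroconvert. The executive summary likewise defines the endpoint as "Rate of seroconversion of neutralizing antibodies against each HPV vaccine genotypes namely 6/11/16/18/31/33/45/52/58" and places the 80% threshold on ARM A alone. The endpoint is assessed at month 7 in women seronegative at baseline.

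The sample size is in Design of the study. The method is "comparing two independent proportions (1:1 allocation in a non-inferiority trial) by a Pearson Chi-square test". The assumed rates are given as "If we consider 95% rate of seroconversion for ARM B (3 doses vaccines) and 80% for ARM A (2 doses vaccines"). For the error rates, without naming one or two sides, the section sets a "significance level test of 0.05 (alpha) and an 80% statistical power (Beta"). The result is "we found that 60 patients per" arm, 120 in total, and then "We would then need in total 150 women to be randomized taking into account the possibility of follow-up lost".

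The same section expects at least 80% seroconversion after two doses and calls 80% an acceptable minimum. It also records that 102 women were randomised instead of 150. The protocol gives no rates by genotype, no correlation between genotypes, no expected number of seronegative women per genotype, and no probability that all nine genotypes pass.

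**The concern.** The power statement and the decision rule describe different events. One is a single comparison of two proportions. The other is a conjunction of nine threshold conditions on ARM A. An all-must-pass rule needs no alpha correction, but the chance of success is the joint probability of nine passes. In addition, the ARM A rate used for sizing equals the threshold, so even a single genotype is close to a coin toss at that rate.

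What is at stake is how a miss is read. A reader who sees 80% power may take failure in one genotype as evidence against two doses. If true rates lie in the low to mid 80s, a range the protocol itself accepts, such a miss is likely by chance alone.

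**Working it through.** **1. Reproduce the protocol's figure.** Inputs from Design of the study: p_B = 0.95, p_A = 0.80, alpha 0.05 (sidedness not stated), power 0.80. The mean rate is 0.875.

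n = [z_α √(2 × 0.875 × 0.125) + z_β √(0.95 × 0.05 + 0.80 × 0.20)]² / 0.15²

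- With z_α = 1.645 (one-sided) and z_β = 0.842, n = 59.05, hence 60. Power at 60 is 80.6%.
- Other variants do not give 60. One-sided with continuity correction gives 72; two-sided gives 76, or 88 with correction. A non-inferiority formula with an assumed 15-point margin (95 minus 80) and 95% in both arms gives 27 (one-sided 0.05) or 34 (one-sided 0.025).
- 120 / (1 − 0.20) = 150, so the inflation corresponds to 20% loss.

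The figure is sound arithmetic for a one-sided test of difference on one pair of rates. Its 80% is the probability of detecting that ARM A is worse when the true rates are 95% and 80%.

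**2. One genotype under the rule as written** (observed ARM A rate at least 80%). P(pass) = P(X ≥ r), with X binomial(n, p) and r the smallest integer ≥ 0.8n. For n = 60, r = 48. For n = 51 (102/2, equal split assumed), 0.8 × 51 = 40.8, so r = 41.

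**3. All nine genotypes.** Under independence the joint chance is P(pass)⁹. Otherwise it was simulated with an exchangeable latent normal variable per woman, correlation 0.5 or 0.8 (10,000 simulated trials), with the same true rate for every genotype. The correlations are assumptions; the protocol gives none.

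| n in ARM A | True rate | One genotype | All nine: independent | corr. 0.5 | corr. 0.8 |
|---|---|---|---|---|---|
| 60 | 80% | 57.6% | 0.7% | 7.8% | 18.0% |
| 60 | 85% | 89.4% | 36.4% | 51.4% | 63.1% |
| 60 | 87.5% | 96.8% | 74.5% | 80.1% | 85.0% |
| 60 | 90% | 99.4% | 95.0% | 95.6% | 96.8% |
| 60 | 95% | >99.9% | >99.9% | about 100% | about 100% |
| 51 | 80% | 55.6% | 0.5% | 6.5% | 16.4% |
| 51 | 85% | 86.7% | 27.6% | 44.2% | 56.6% |
| 51 | 87.5% | 95.2% | 64.4% | 71.8% | 79.0% |
| 51 | 90% | 98.9% | 90.6% | 91.9% | 93.3% |
| 51 | 95% | >99.9% | >99.9% | about 100% | about 100% |

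The joint chance can never exceed the single-genotype chance. At a true 80% it is therefore capped at 57.6% (n=60) or 55.6% (n=51) whatever the correlation.

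**4. Where the joint chance reaches 80%.** For n = 60 this happens at a true rate of about 87-88% in every genotype (independence at 88% gives 80%). For n = 51 it is about 88-89%: at 88% the joint chance is 71%, 77% and 83% for the three correlations, and at 89% it is 83%, 87% and 89%.

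**5. Fewer evaluable women.** Restriction to baseline-seronegative women reduces n by an amount the protocol does not give. Under independence at a true 90%, the joint chance is 91% with n = 51, 87% with n = 40 and 79% with n = 30.

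**6. Sensitivity only: a margin-based test.** The protocol states no margin and no confidence-limit test. With an assumed 15-point margin, 95% in both arms, 51 per arm and independent genotypes, the joint chance runs from 25% (Newcombe, two-sided 95% limits) to 74% (normal approximation, one-sided 0.05). It depends heavily on the method.

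**The case against.** The strongest reply is that the protocol expects at least 80% in ARM A, which is a floor and not a point prediction. If two doses perform close to the 95% expected of three, the rule as written is almost certain to be met: over 99.9% at a true 95%, and at least about 91% at a true 90% with 51 women. This stands. A reader might infer that the trial's chance of success is far below 80% whatever the truth, and the documents do not support that.

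A reader might also raise the stated power to the ninth power (0.8⁹ = 13%), or treat the 80% as power per genotype. Both are wrong. Step 1 shows that the 80% is power to find a difference, and at the sizing rate a single genotype passes only about 58% of the time.

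It can further be said that randomisation is over, that the 80% was attached to 60 per arm and never claimed for 51, and that no passage says a missed genotype proves two doses inferior. All true. The correction changes no patient number, and the risk of misreading is a risk, not something the protocol asserts. Presentation of intervals may also sit in an analysis plan that is not shown. What remains is that the protocol itself states both a power and a success rule, and the first does not describe the second.

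**Conclusion.** The point holds in a conditional form. The sample size arithmetic is correct for what it tests, but it does not give the probability of meeting the nine-genotype rule. At the protocol's own ARM A rate of 80% that probability is about 0.5-18% over the correlations examined, and 80% is out of reach at any correlation. At a true 85% it is 36-63% (n=60) or 28-57% (n=51). It passes 80% only when every genotype's true rate is about 87-89%, depending on n and correlation.

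These figures assume a common true rate across genotypes, an exchangeable latent correlation between 0 and 0.8, and 60 or 51 evaluable women in ARM A for each genotype. The issue is power and interpretation; requiring all nine to pass does not inflate the type I error.

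**What to change.** In Design of the study, state that the 80% is power for one comparison of 95% with 80% at 60 per arm, and that it is neither per-genotype nor overall power for the decision rule. Replace or supplement it with the joint probability of meeting the nine-genotype rule at the number actually randomised. Show this over a stated range of true ARM A rates (80-95%) and between-genotype correlations, with an allowance for women already seropositive. Any margin-based figures should appear only as a sensitivity range, unless a margin and a confidence-limit test are added to the protocol.

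In Primary outcome, state that missing the criterion for a genotype means non-inferiority was not shown for that genotype, not that two doses are inferior.

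The cost is a short simulation and a few sentences. No extra patients are needed. The price is a less favourable stated power at true rates in the low to mid 80s.

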### **Secondary outcomes**

1/Safety and tolerability of the vaccines will be evaluated by a specific questionnaire on a phone call made by the research team to the participant and scheduled at least

48 hours and maximum 7 days after each vaccine dose; the questionnaire will evaluate whether there is any complain regarding local reaction (pain, redness, swelling, pruritus), systemic reaction (fever, malaise and fatigue) or other side effect. In case of any usual complain > mild stage, or the presence of an unusual complain, the patient will be assessed by a visit and physical examination performed by the research team. The questionnaire has been elaborated according to the published data on safety evaluation of the ninevalent vaccine [24].

2/ The potential impact of vaccine administration on T-lymphocyte CD4+ cell count and HIV viremia will be assessed by measuring CD4 cell count and HIV viremia at baseline (any measure within 6 months before screening can be taken into account) and month 7. Any detectable HIVRNA >1000 cp/ml will be reassessed on a second samples taken 2-4 weeks later. Any significant decrease in T-lymphocyte CD4+ cell count (defined as a decrease by more of 5% in the percentage or >100 cells/ $\mu$ l) will be reassessed on a second sample taken 2-4 weeks later.

3/ measure of the title of specific neutralizing antibodies against each HPV vaccine genotypes (6/11/16/18/31/33/45/52/58), at baseline, month 7 (i.e., 1 month after 2 or 3 doses) by the cLIA technique and at month 18 ( 12 months after vaccination completion in 200 HIV-positive women by the IgG LIA technique [30].

4/ The cellular immune response will be evaluated in a subset of 40 patients, 20 per arm, (aged 18-40 years old) by measuring specific CD4+T cells expressing CD40, IL2, IFN-g or TNF-alpha against HPV 16/18/31/52 and 58. The analysis will be performed on a PMBC sample of 30 to 50 ml taken at baseline and at month 7 (see Procedures for Collection and Handling of Study Specimens section); a separate IC has to be signed for this sub-analysis.

4/ The incidence and prevalence rates of HPV infections and of abnormal cervical cytology performed by PCR and cytology will be done on cervical swab taken by the gynecologist at baseline and month 18. Cervical cytology and HPV infection will be assessed by the national reference centre for HPV (AML, Antwerpen) [32]. The

baseline gynecological sample might have been taken up to 6 months before the vaccination. These swabs will be sampled in all participants with previous vaginal sexually activity. In case of no previous vaginal sexual intercourse, the samples will not be taken.

#### 5/Completion of the vaccine schedule

Comparison of the proportion of women achieving full course of vaccine administration in each arm, namely for ARM A receiving 2 doses and for ARM B receiving 3 doses.

6/ Proportion of patients needing a booster dose (*i.e.*..a third dose) in ARM A  
If after 2 doses of vaccine (ARM A), the month 7 antibodies analysis shows absence of seroconversion against one of the HPV genotypes contained in the vaccine, the participant will receive a third booster dose.

7/ Impact of basal immune activation (levels of CD25, sCD14, IP-10, IL-6, TNF- $\alpha$ , d-Dimers, CRP) on the seroconversion rate and long term antibody persistiance

### **Randomisation**

We will generated a randomization schedule with the classical method of block randomization. In practice, for this study with two arms, 75 patients each, we will decide a number of blocks of 25, with block size of 6. We will use SAS programming and SAS PROC PLAN for the generating randomization schedules (version 9.4 SAS institute, Cary North Carolina, USA).

### Amendment after Coronavirus crisis

1.Due to the COVID-19 health crisis in Belgium including a lockdown between March 15th 2020 and June 2020, some patients could not attend their scheduled appointments for this study. Moreover, the routine gynecological consultation was closed during the two-months lockdown. Now that the routine gynecological has

reopened, it is busier than usual as patients that have missed their appointments need to be seen. The initial study protocol stated that the first vaccination dose should be performed within 6 months after the baseline cervical sample. In order not to repeat the baseline cervical sample in an already full consultation, we propose to extend this time lapse to 12 months.

In the same way, we propose to extend the last serum and cervical samples delay to 18 months after the last vaccine dose (initially to be performed 12 months after last vaccination dose) so the 18-months visit can be postponed up to 24 months after first vaccination dose.

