**Etude Papillon**

Phase IV prospective study evaluating the reactogenicity and immunogenicity (both humoral and cellular responses) and the safety of the 9valent vaccine against HPV (Gardasil9®Merck) in HIV-positive women aged 15-40 years with fully suppressed HIV viremia on combined antiretroviral therapy. After a first open phase evaluating tolerability of Gardasil9, women will be randomized between two different doses schedules: in the first schedule, women will receive 2 doses at time 0 and 6 months and a third dose between 18-48 months if their antibody levels are insufficient; the second schedule will be 3 doses at 0, 2 and 6 months. Primary outcome is the non-inferiority of the rate of seroconversion against each HPV vaccine genotypes in women seronegative at baseline after either 2 or 3 doses of vaccination (month 7). Secondary outcomes are rate of seroconversion after 3 doses if they have received a third dose, completion of vaccine schedule, vaccine safety, antibody titles, and induction of cellular immunity against HPV contained in the vaccine, incidence of cervical HPV infection and incidence of abnormal cytology after vaccination.

Date: 15/12/2023

Author: [name] and [name] [name]

Version: 7

NCT NCT03391921

EUDRACT 2018-000228-33

FAMHP: FADG/R&D/BEN/mmn

Centre de Référence SIDA

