## Rationale

In women, persistent infection with high risk (HR) Human papillomavirus (HPV) is responsible for the development of high grade cervical, vulvar or vaginal intraepithelial neoplasia (HGCIN, HGVIN, HGVAIN) and invasive cervical cancer (ICC). Worldwide, HPV 16 and 18 represent respectively 50 and 20% of all HRHPV genotypes responsible for ICC [1]. Prophylactic vaccination against HPV 16 and 18 in adolescent and young women aged 16-26 years has been shown to be highly efficient in preventing both infection with these genotypes of HRHPV and HPV-associated lesions such as HGCIN, HGVIN, HGVAIN due to vaccine types (prevention of >90%) [2-4]. Vaccination of women aged 26-45 years is also efficient with around 80% of prevention for both infections and lesions related to vaccine HPV types [5-6].

HIV-positive women are more frequently infected with persistent HRHPV and suffer significantly more from HPV-associated diseases such as ICC (6 to 10 times more frequent than in the general population) and precancerous lesions. Their dysplastic lesions are more severe and they have a worst outcome after treatment [7-8].

We have conducted a prospective longitudinal study on HRHPV infection and HPV-associated diseases in a cohort of almost 900 HIV-positive women living in Belgium. We found that HRHPV infection was highly prevalent (43%) with a high incidence of new infections (13/100 women-year) [9-10]; 28% had cervical intraepithelial abnormal cytology and 3% had HGCIN compared to respectively 6% and 1.2% in the general Belgian population. We also showed that the most prevalent HPV genotypes were HPV 52 (20%), HPV 18 (15%), HPV 31/35/51/58 (12% each) and HPV 16% (9.5%)[11]. This genotypic distribution is different from the general population and is attributable first to HIV-infection which is a known risk factor for more frequent infection with HPV other than 16 or 18 and second with the African origin of most women followed for HIV in Belgium (similar genotype distribution is found in women living in sub-Saharan African countries).

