## Flowchart

### To be performed at baseline:

- Informed consent(s) signature
- Measure of serum antibodies against HPV 6/11/16/18/31/33/45/52/58 (1 10 ml tube) by 9cLIA by Merck USA.
- Measure of lymphocytes T CD4+ level and HIV viremia if there is no previous sample up to 6 months before baseline.
- Cervical smear on a liquid based samples (Cytoprep) taken by the gynecologist for cytology and HPV detection (to be performed by the national reference centre for HPV, AML, Antwerpen) if there is no previous sample up to 6-12 months before baseline. These samples will not be taken if the participant has never experienced vaginal sexual intercourse.
- ONLY FOR THE CELLULAR IMMUNE RESPONSE SUBSTUDY: an additional specific IC should be signed and a sample of 50-100 ml should be taken.
- Randomisation (after December 2018 amendment): patients will be allocated to one of the two arms by random randomization through a software program. The result of the allocation will be known to the patient, to his healthcare providers and to the study team.
  - ARM A: vaccination at time 0 and 6 and a later booster if **needed**
  - ARM B: vaccination at time 0, 2 and 6 months
  - **Vaccine administration after randomisation**

Gardasil9 (Merck®) first dose will be administrated intramuscularly in the deltoid while the patient is lying down. The patient will remain lying 15 minutes after the injection.

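### Cervical HPV and cytology incidence labelled as arising after vaccination is counted from a baseline swab that may precede dose 1 by up to 12 months, so absolute incidence is overstated

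*Protocol*

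**What the plan says.** The title-page summary lists among the secondary outcomes the "incidence of cervical HPV infection and incidence of abnormal cytology after vaccination". The body text on Secondary outcomes (the second of two items numbered 4) bases this on PCR and cytology from a "cervical swab taken by the gynecologist at baseline and month 18". The Executive summary places the second swab 12 months after the end of vaccination.

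The protocol gives different limits for the timing of the first swab:

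- Secondary outcomes, same item: "baseline gynecological sample might have been taken up to 6 months before the vaccination".
- Amendment after Coronavirus crisis, item 1, first recalls the old rule: "The initial study protocol stated that the first vaccination dose should be performed within 6 months after the baseline cervical sample". It then widens it: "we propose to extend this time lapse to 12 months".
- Flowchart, baseline visit: a new smear is needed only "if there is no previous sample up to 6-12 months before baseline".

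The last swab has moved too. Item 1 of the amendment states that "the 18-months visit can be postponed up to 24 months after first vaccination dose", and the Flowchart heads that visit month 18-24. No other cervical sample is scheduled, either at the time of dose 1 or at the end of the vaccine course. No rule separates infections acquired before dose 1.

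**The concern.** With two swabs per woman, a new infection is known only to have arisen somewhere between them. If the first swab was taken well before dose 1, part of that interval is unvaccinated time. A woman infected in those months tests negative at the first swab and may test positive at the last. She is then counted as an incident case after vaccination, although vaccination could not have prevented that infection. The same applies to abnormal cytology.

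The amendment justifies the wider window by clinic workload and does not mention its effect on this outcome. At stake is the absolute incidence that the trial will report for vaccinated women with HIV, which readers may set against other vaccinated or unvaccinated cohorts.

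**Working it through.** **Timeline.** The last scheduled dose is at month 6. The original final swab falls at 6 + 12 = month 18 and the postponed one at 6 + 18 = month 24. Both agree with the protocol. The swab-to-swab interval is the gap before dose 1 plus the time from dose 1 to the final swab. With the original 6-month limit and a month-18 swab it is 18 to 24 months. With both extensions it is 18 to 36 months. Pre-dose time can be 6 of 24 months (25%) under the original rules. Under the amended rules it can be 12 of 30 (40%) with a month-18 swab, or 12 of 36 (33%) with a month-24 swab.

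**Rate.** For the sponsor's own cohort of HIV-positive women the Rationale reports a "high incidence of new infections (13/100 women-year", which refers to high-risk HPV. I assume a constant hazard, no clearance before the final swab and, at first, no vaccine effect. Cumulative risk over *t* years is 1 − exp(−0.13 *t*).

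| Period | Calculation | Risk |
|---|---|---|
| 6-month gap | 1 − exp(−0.065) | 6.3% |
| 12-month gap | 1 − exp(−0.130) | 12.2% |
| Dose 1 to month 18 | 1 − exp(−0.195) | 17.7% |
| 12-month gap + 18 months | 1 − exp(−0.325) | 27.7% |

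A woman at the 12-month limit with a month-18 final swab therefore contributes a risk of 27.7% to a quantity that should be 17.7%. Of the new acquisitions, 12.19 / 27.75 = 44% predate dose 1. With the final swab at month 24 the share is 38%.

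**Sensitivity to the rate.** The documents give one rate, so I take 5 to 20 per 100 woman-years as an assumed range. The pre-dose risk over 12 months is then 4.9% to 18.1%. The reading is 11.8% instead of 7.2% at the low end, and 39.3% instead of 25.9% at the high end.

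**Sensitivity to vaccine effect.** Suppose vaccination halves the rate from dose 1 (an assumption). With a 12-month gap and a month-18 swab, the reading is 20.3% instead of 9.3%, and 60% of acquisitions predate dose 1. With an 80% reduction it is 15.5% instead of 3.8%, and 78%. The mislabelled share grows as the vaccine works better.

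**Abnormal cytology.** The protocol gives a prevalence but no incidence rate, so I put no figure on this part.

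**The case against.** The case on the other side has several parts.

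- *The figures are extremes.* This stands. They place women at the full 12-month gap and ignore clearance, although infections acquired before dose 1 have the longest time to clear before the last swab. Actual gaps are not given.
- *The words about incidence after vaccination appear in the title-page summary. The outcome definitions name only two sampling times and do not fix a proportion.* This is true, and the body speaks of rates. A rate does not remove the problem, though. With a 12-month gap, an 18-month follow-up and an assumed halving of the rate, the rate over the whole interval is (12 × 13 + 18 × 6.5) / 30 = 9.1 per 100 woman-years, against 6.5 after dose 1.
- *Person-time and sensitivity analyses belong in a statistical analysis plan.* In general they do. But the protocol itself fixes the window, the two-swab schedule and the label, and no later analysis can recover the date of acquisition.
- *The 6-month rule had the same weakness.* It did. The amendment doubles the permitted gap.

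A reader might go further and infer that the comparison of two with three doses is confounded by time at risk. The documents do not support that as stated. Arms A and B were randomised concurrently, so the gap should balance between them, and the definitions of this outcome specify no comparison between groups. Permitted maxima do differ by enrolment date. Open-phase women (June 2018 to January 2019) were under the 6-month limit, third-phase women (from 25 February 2021) are under the 12-month limit, and the randomised phase spans the change. This matters only if incidence is compared by number of doses in the whole cohort.

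Nor is 18 against 36 months a contrast between phases, since 18 months is permitted in every phase. Open-phase women reached month 18 between December 2019 and July 2020, so some final visits may also have been postponed. The phase maxima are then 6 + 24 = 30 against 12 + 24 = 36 months, or 27.7% against 32.3% at the same hazard. Without postponement in the open phase they are 24 against 36 months, or 22.9% against 32.3%.

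**Conclusion.** The point holds for absolute incidence. Following the protocol as written places infections that may predate dose 1 in an outcome described as arising after vaccination, and two swabs cannot separate them. The direction is upward. At the limit of the window, at 13 per 100 woman-years with constant hazard, no clearance, no vaccine effect and a month-18 final swab, the overstatement is about 10 percentage points (27.7% against 17.7%). In practice it will be smaller to the extent that gaps are shorter than 12 months and early infections clear.

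The primary outcome is unaffected, and no bias in the randomised comparison is shown. The 6-month and 12-month limits in the current text contradict each other, as do the month-18 and month-18-24 timings of the final swab. This is a correction worth making to one secondary outcome; it does not threaten the trial.

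**What to change.** 1. Report incidence per woman-years between the actual baseline and final swab dates, treated as interval-censored. Label it as incidence between those swabs and state that it includes time before dose 1. Do not describe it as incidence after vaccination, because this denominator still mixes unvaccinated and vaccinated time.
2. Add a sensitivity analysis restricted to women whose baseline swab was at most 6 months before dose 1. It costs some precision and reduces the bias without removing it: the pre-dose risk at a 6-month gap is still 6.3%.
3. If incidence is compared by number of doses in the whole cohort, account for the gap from swab to dose 1 and for the swab-to-swab interval.
4. Reconcile the 6-month window under Secondary outcomes with the amendment and the Flowchart. Reconcile the final-swab timing in the Executive summary and under Secondary outcomes with the amendment and the month 18-24 visit.

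No new sampling is needed. The cost is analysis and wording, provided that the dates of swabs and doses were recorded, which the protocol does not state explicitly.
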